7. MANAGEMENT OF TOXICITY

7.1 Acute Toxicity

Acute morbidity potentially associated with therapy will be monitored and recorded on the Radiation Oncology On-Treatment Evaluation Form for all patients from baseline to 3 months after completion of radiation therapy. Grading will be according to the RTOG Acute Morbidity Scoring Criteria as follows:

Organ	Grade 0	Grade 1	Grade 2	Grade 3	Grade 4
Skin	No change	Faint	Tender or	Confluent,	Ulceration,
	over	erythema,	bright	moist	hemorrhage,
	baseline	epilation, dry	erythema,	desquamation	necrosis
		desquamation,	patchy moist	other than skin	
		or decreased	desquamation,	folds, pitting	
		sweating	moderate	edema	
			erythema		
Eye No change		Mild	Moderate	Severe keratitis	Loss of vision
	over	conjunctivitis	conjunctivitis	with corneal	(unilateral or
	baseline	with or	with or	ulceration,	bilateral)
		without	without	objective	
		scleral	keratitis	decrease in	

Organ	Grade 0	Grade 1	Grade 2	Grade 3	Grade 4
		injection,	requiring	visual acuity or	
		increased	steroids	in visual fields,	
		tearing	and/or	acute	
			antibiotics,	glaucoma,	
			dry eye	panopthalmitis	
			requiring		
			artificial tears,		
			Initis With		
For	No ohongo	Mild avtornal	Moderate	Savara avtarnal	Daafnass
Lar	over	otitis with	external otitis	otitis with	Deamess
	baseline	erythema	requiring	discharge or	
	basenne	nruritis	topical	moist	
		secondary to	medication	desquamation	
		dry	serous otitis	symptomatic	
		desquamation	media.	hypoacusis.	
		not requiring	hypoacusis on	tinnitus, not	
		medication.	testing only	drug related	
		Audiogram			
		unchanged			
		over baseline.			
CNS	No change	Fully	Neurologic	Neurologic	Serious
	over	functional	findings	findings	neurologic
	baseline	status with	present	requiring	impairment
		minor	sufficient to	hospitalization	which included
		neurologic	require home	for initial	paralysis,
		findings, no	care. Nursing	management	coma, or
		medications	care may be		seizures,
		needed	required.		despite
			including		Hospitalization
			steroids		required
			and/or anti-		required
			seizure agents		
Hematologic	> 4 0	30-<40	20 - <30	10-<20	<1.0
WBC		2	2.0 2.0		1.0
(x1000)					
Platelets	≥ 100	75 - <100	50 - <75	25 - <50	<25 or
(x 1000)					spontaneous
					bleeding
Neutrophils	≥ 1.9	1.5 - <1.9	1.0 - <1.5	0.5 - <1.0	<0.5 or sepsis
Hematocrit	\geq 32	28 - <32	<28	Packed cell	N/A
(%)				transfusion	
				required	

7.2 Late Toxicity

Late toxicity will be recorded on the Radiation Oncology Follow-up form at each follow-up visit greater than 3 months post completion of radiation therapy. Grading will be according to the RTOG Late Radiation Morbidity Scoring Schema as follows:

Organ	Grade 0	Grade 1	Grade 2	Grade 3	Grade 4	Grade 5
Skin	None	Slight atrophy, pigmentation change, some hair loss	Patchy atrophy, moderate telangiectasia, total hair loss	Marked atrophy, gross telangioectasia	Ulceration	
Subcutaneous Tissue	None	Slight induration and loss of subcutaneous fat	Moderate fibrosis but asymptomatic . Slight field contracture. <10% linear reduction	Severe induration and loss of subcutaneous tissue. Field contracture >10% linear measurement	Necrosis	Death direct
Spinal Cord	None	Mild L'Hermitte's syndrome	Severe L'Hermitte's syndrome	Objective neurologic findings at or below cord level treated	Mono-, para-, quadra-plegia	lly related to la
Brain	None	Mild headache, slight lethargy	Moderate headache, great lethargy	Severe headaches, severe CNS dysfunction (partial loss of power or dyskinesia)	Seizures, paralysis, coma	te radiation effect
Eye	None	Asymptomati c cataract, minor corneal ulceration of keratitis	Symptomatic cataract, moderate corneal ulceration, minor retinopathy or glaucoma	Severe keratitis, severe, retinopathy or detachment, severe glaucoma	Panopthalmitis, blindness	

8. STATISTICAL CONSIDERATIONS

8.1 Study Design/Endpoints

8.1.1 Study Design

This is a single arm prospective investigation to evaluate the local recurrence rate in the spared NPC-containing regions of the brain after NPC-sparing radiation therapy plus temozolomide for newly diagnosed GBM.

8.1.2 **Primary Endpoint**

Site of local recurrence at 1 year post radiation therapy will be recorded for each patient. Sites will be classified as follows: 1) Recurrence within the spared NPC-containing region, defined as a recurrence within the avoidance structure contoured on the simulation CT scan; 2) Recurrence outside of the spared NPC-containing region, defined as a recurrence that is not within this avoidance structure; 3) No local recurrence.

8.1.3 Secondary Endpoints

- 8.1.3.1 The extent of NPC-sparing will be recorded for each patient. Patients will be binned into 4 groups according to the volume of NPC region that receives a certain dose as follows: 1) V_{5Gy}≤50%; 2) V_{5Gy}≤20%; 3) V_{10Gy}≤20%; 4) Doses higher than levels 1-3.
- 8.1.3.2 The X-, Y-, and Z- coordinate distances in centimeters will be recorded from the most proximal point of the planning tumor volume to the closest point of the spared NPC-containing niche. The mean, minimum, and maximum radiation dose to the spared NPC-containing region will be recorded for each patient. In addition, the volume of the "NPC_for_sparing" region will be recorded.
- 8.1.3.3 Completion of neurocognitive testing and Neurocognitive function will be assessed at baseline, and at six, twelve, and twenty-four months from baseline using the Mini Mental State Exam, Trail Making Test A & B, Controlled Oral Word Association Test, Hopkins Verbal Learning Test-Revised and the Digit Symbol Substitution Test.

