1.2. Secondary Objectives

- 1.2.1 To quantify the extent of radiation dose sparing to the NPC containing regions that is possible without compromising tumor coverage in patients with newly diagnosed GBM
- 1.2.2 To examine the relationship between radiation dose to the NPC-containing niches and the proximity of the planning tumor volume to the NPC-containing regions.
- 1.2.3 To assess feasibility of evaluating cognitive function prospectively in patients undergoing NPC sparing RT for newly diagnosed GBM.
- 1.2.3 To explore if the potential change from baseline to six months in neurocognitive function as measured by the Mini Mental State Exam, Trail Making Test, Controlled Oral Word Association test (COWAT), Hopkins Verbal Learning Test-Revised, Digit Symbol Substitution Test is related to radiation dose to the NPC containing regions in patients treated with NPC sparing radiation for newly diagnosed GBM.

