5.2.4 Neural Progenitor Cell Containing Niches

The NPC containing niches will be defined as a 5 millimeter region adjacent to the lateral wall of the lateral ventricle and the entire hippocampus. These areas will be contoured on the simulation CT scan using a manually coregistered MRI as a reference. A portion of the NPC-containing niches which is >2 cm from the PTV will be contoured as a region of interest and labeled as "NPC_for_sparing". A radiation treatment plan will be generated in which we attempt to limit the RT dose to the "NPC_for_sparing" region as much as possible without compromising the radiation dose coverage of the tumor. Specifically, using inverse planning, the dose constraint and weight of the "NPC_for_sparing" region will be progressively tightened until additional iterations would to result in compromised tumor coverage or unacceptable dose to another organ at risk. The extent of NPC sparing that is possible will be recorded for each patient in terms of the volume of the "NPC_for_sparing" region, and the mean, minimum, and maximum dose to this area.

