To assess the feasibility of evaluating cognitive function prospectively in this patient population, we will evaluate the six month post radiation therapy protocol compliance in terms of neuropsychological evaluations. The proportion of patients completing the planned neurocognitive assessments at both baseline and 6 months post radiation therapy will be calculated, along with the 95% confidence interval. If \geq 40% of patients did not complete at least 1 of these planned assessments, the testing will be considered not feasible.

The change in neurocognitive function from baseline to 6 months post radiation therapy will be explored by using the 5 instruments measuring neurocognitive function. The change will be summarized graphically (using, for example, boxplots) and using mean, median or score shifting etc. This will be done for each instrument separately. Correlation coefficients will be calculated to explore potential correlation between the change in neurocognitive function from the baseline and the radiation dose to the NPC-containing region.

Spearman's rank correlation coefficient will be calculated to explore an association between the closest distance (either X-, Y-, or Z-) of the planning tumor volume to the spared NPC-containing niche and the mean, minimum, and maximum radiation dose to this region.

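### Objective 1.2.2 asks about PTV proximity to the niches, but distance and dose are measured only on niche tissue more than 2 cm from the PTV, so the planned correlations cannot rank tumors closer than that

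*Combined protocol and SAP*

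**What the plan says.** Secondary objective 1.2.2 is to examine "the relationship between radiation dose to the NPC-containing niches and the proximity of the planning tumor volume to the NPC-containing regions". Both sides of that relationship refer to the niches as a whole.

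Section 5.2.4 defines the niches as "a 5 millimeter region adjacent to the lateral wall of the lateral ventricle and the entire hippocampus". It then carves out a sub-structure: "A portion of the NPC-containing niches which is >2 cm from the PTV will be contoured as a region of interest", labeled `NPC_for_sparing`. The primary endpoint (8.1.2) ties the word spared to that contour: "Recurrence within the spared NPC-containing region, defined as a recurrence within the avoidance structure contoured on the simulation CT scan".

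The measurements for 1.2.2 are in 8.1.3.2. "The X-, Y-, and Z- coordinate distances in centimeters will be recorded", running "from the most proximal point of the planning tumor volume to the closest point of the spared NPC-containing niche". Mean, minimum and maximum dose are recorded for the spared region, along with the volume of `NPC_for_sparing`. Section 8.4 then plans Spearman coefficients between the closest distance on any one of the three axes, from the "planning tumor volume to the spared NPC-containing niche and the mean, minimum, and maximum radiation dose to this region". Neither section lists a distance to the uncut niche, or its mean, minimum or maximum dose.

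**The concern.** The objective names one structure and the endpoint measures another. The measured structure is defined by its distance from the tumor, and that same distance then serves as the explanatory variable. Selecting tissue by distance and then measuring distance to what remains puts a floor under the measure at the selection threshold.

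The patients affected are those whose PTV overlaps, touches or lies within 2 cm of a niche. If they are a large part of the 30, the planned coefficients say little about proximity to the niches. A weak correlation could then be read as evidence that proximity hardly matters to niche dose, when it partly reflects the contouring rule. Dose has a parallel problem, because the niche tissue nearest the tumor is removed before dose is summarized.

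**Working it through.** The plan gives no figure for this objective (no power, precision or expected correlation), so there is nothing to reproduce. The check is of definitions first, then of size.

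**1. The floor.** Let N be the whole niche and d(p) the straight-line distance from a niche point p to the PTV. Under 5.2.4 the spared structure is S = {p in N : d(p) > 2 cm}.
- True proximity is D = min d(p) over N, and can be 0.
- Distance to the spared structure is D_S = min d(p) over S, and cannot be below 2 cm.
- If a continuous part of N crosses the 2 cm shell around the PTV, D_S is about 2 cm whatever D is. A PTV touching the ventricular wall (D = 0) and one at D = 1.9 cm both give D_S of about 2 cm.
- If D > 2 cm nothing is cut, and D_S = D.
- If one niche lies wholly within 2 cm, the nearest spared point is on another niche and D_S can exceed 2 cm.

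**2. What the recorded components hold.** The plan records x, y and z, not D_S. With D_S at about 2 cm, x² + y² + z² ≈ 4 cm². Each component can lie anywhere from 0 to 2 cm, and the smallest is at most 2/√3 = 1.15 cm. A displacement of (2, 0, 0) has a smallest component of 0, while (1.15, 1.15, 1.15) has 1.15. Both are 2 cm long, so the difference is direction only.

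**3. Illustration by simulation (assumed geometry, not from the documents).** 4,000 spherical PTVs of radius 1.5 to 4 cm were placed at random around box-shaped periventricular strips and hippocampi on both sides. In this model 3,972 PTVs had D ≤ 2 cm. That share is a product of the assumed geometry and does not estimate the trial's.

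| Among PTVs with D ≤ 2 cm | 5th percentile | Median | 95th percentile | Maximum |
|---|---|---|---|---|
| D, whole niche (cm) | 0 | 0 | 1.25 | 2.00 |
| D_S, spared part (cm) | 2.00 | 2.00 | 2.01 | 2.52 |
| Smallest of x, y, z (cm) | 0.03 | 0.41 | 0.94 | 1.15 |

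The single components had medians of 0.87, 1.26 and 0.93 cm. Among the 1,113 PTVs off the niche but within 2 cm, the Spearman correlation with D was 0.06 (X), -0.21 (Y), 0.03 (Z) and -0.16 (smallest component). The fraction of the niche that was spared correlated with D at 0.69.

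**4. Ceiling for a straight-line distance.** Suppose a share f of patients is tied at the floor. On a scale where untied ranks have variance 1/12, the tied variable has rank variance (1 - f³)/12. The largest possible covariance with an untied variable equals that same quantity. The largest Spearman coefficient is therefore √(1 - f³):
- f = 50% (15 of 30): √(1 - 0.125) = 0.94
- f = 70% (21 of 30): √(1 - 0.343) = 0.81
- f = 90% (27 of 30): √(1 - 0.729) = 0.52

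The values of f are assumptions. The ceilings describe D_S and not the X/Y/Z variables that the plan correlates.

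**The case against.** A reader might infer that the predictor has no variation, or that every close tumor will be recorded at 2 cm. The documents do not support that. The plan records axis components, and these differ between patients. The ceilings in step 4 are thus not predictions for the planned coefficients. What remains is that the variation in the components mainly reflects direction.

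The 2 cm floor also depends on two readings. Section 8.1.3.2 uses three labels within one item (spared niche, spared region, `NPC_for_sparing`), so their identity is inferred, although 5.2.4 and 8.1.2 support it. Section 5.2.2 defines an initial and a cone-down volume, each with its own PTV, and the plan does not say which sets the cut or the distance. If they differ, some variation returns, but it would reflect the difference between the two volumes, and whole-niche distance would still be missing.

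Studying dose in the structure that is actually optimized is coherent and fits objective 1.2.1. It would also be wrong to say that proximity limits sparing mainly between 0 and 2 cm, since 5.2.4 attempts sparing only beyond 2 cm. These points justify keeping the spared-structure measures. They do not make those measures an answer to 1.2.2 as worded.

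Finally, some information is already collected. The recorded volume of `NPC_for_sparing` is likely to carry proximity information, as the 0.69 above suggests, but 8.4 does not use it in this analysis. The dose-volume bins in 8.1.3.1 refer to the NPC region without saying whether the whole niche is meant, and they are not related to distance either.

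**Conclusion.** The point holds in a limited form. Followed exactly, 8.1.3.2 and 8.4 do not measure proximity to the niches for tumors within 2 cm of one, and they leave the nearest niche tissue out of the dose summaries. For those patients the planned Spearman coefficients cannot separate an abutting tumor from one 1.9 cm away.

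This rests on the spared niche being `NPC_for_sparing`, on the same PTV setting both the cut and the distance, and on the cut running through the niche. How much it matters depends on the share of patients within 2 cm, which the documents do not give.

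The consequence is contained. The analysis is exploratory, no decision rule depends on it, and a reader should not infer that the primary endpoint or the treatment plans are affected. The change is worth making because a stated objective otherwise goes unanswered as worded.

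**What to change.** In 8.1.3.2 and 8.4:

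- Add the shortest 3-D distance from a named PTV (state whether initial or cone-down) to the whole contoured niche, and make it the predictor for objective 1.2.2.
- Use a signed distance, negative when the PTV overlaps the niche, or add the PTV-niche overlap volume. Scoring all overlaps as 0 would create new ties. In the illustrative model (3,972 - 1,113)/3,972 = 72% of PTVs within 2 cm touched or overlapped the niche, and a tied share of 0.72 caps Spearman at √(1 - 0.72³) = 0.79.
- Correlate the new distance with mean, minimum and maximum dose to the whole niche, with dose to `NPC_for_sparing`, and with the ratio of `NPC_for_sparing` volume to whole-niche volume.
- Keep the existing spared-structure distance, if wanted, as a descriptive measure.

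The cost is wording in two sections and a small extra readout from the planning system. Section 5.2.4 already has the full niches contoured, so no new imaging, contouring or visits are needed, and values for treated patients can be recovered where plans are kept. Treatment planning is unchanged.

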8.2 Sample Size/Accrual Rate

8.2.1 Sample Size

The required sample size is based upon the primary study hypothesis which is the rate of local recurrence within the spared NPC-containing region at 1 year post radiation therapy in patients treated with NPC sparing RT plus temozolomide for newly diagnosed GBM. Using conventional RT, approximately 20% of GBM recur outside of the tumor bed or radiation field margin (48). We hypothesize that there will be $\leq 25\%$ LR rate in the designated NPC avoidance region using our modified radiation technique, which is clinically acceptable. This is the first study to estimate the LR rate in the spared NPC containing region following NPC sparing RT for GBM. Given the clinically meaningful control LR rate in this region of 25% and a moderate variation among the patients, the 30 patients will have the optimal information gain (relative certainty) based on empirical information entropy to estimate the LR rate in the spared region (49).

8.2.2 Accrual

We anticipate enrollment of approximately 3-4 patients per month to the protocol with accrual completed in approximately 1-2 years.

8.3 Stratification Factors

There will be no stratification factors upon initial enrollment in the protocol.

8.4 Statistical Methods of Analysis

All analysis will be based on the Intend-To-Treat (ITT) principle. Per-protocol will be allowed after ITT analyses.

The proportion of patients with LR in the avoidance region of the NPC will be estimated along with the exact 95% confidence interval. The lower bound 95% confidence interval of exact binomial distribution will be used to determine the acceptance of the LR rate of 25%.

All patients will count towards assessment of all objectives. However, if no patient relapses in the spared NPC containing region, we recognize that the present study will not definitively demonstrate that sparing of the NPC regions does not impact the pattern of recurrence since this is a pilot study and 2 patients received mebendazole following completion of radiation therapy but prior to relapse. Given that no intervention to date including systemic agents, radiation dose escalation, and hypofractionation has ever impacted the site of recurrence we feel it is exceedingly unlikely that mebendazole would impact our primary endpoint. However, we will evaluate if the analysis of the primary endpoint would yield different results with or without inclusion of these patients. If there is a difference both analyses will be presented in the manuscript. Even if there is no statistically significant difference

between the groups we will clearly state in our publications that 2 patients received mebendazole with their adjuvant temozolomide following completion of radiation therapy but prior to relapse.

To quantify the extent of radiation dose sparing to the NPC containing regions that is possible, patients will be binned into 4 groups according to the volume of NPC region that receives a certain dose as follows: 1) $V_{5Gy} \le 50\%$; 2) $V_{5Gy} \le 20\%$; 3) $V_{10Gy} \le 20\%$; 4) Doses higher than levels 1-3. The proportion of overall patients who meet at least the dose constraint will be estimated using a binomial distribution along with 95% confidence intervals, as well as the individual group.

To assess the feasibility of evaluating cognitive function prospectively in this patient population, we will evaluate the six month post radiation therapy protocol compliance in terms of neuropsychological evaluations. The proportion of patients completing the planned neurocognitive assessments at both baseline and 6 months post radiation therapy will be calculated, along with the 95% confidence interval. If \geq 40% of patients did not complete at least 1 of these planned assessments, the testing will be considered not feasible.

The change in neurocognitive function from baseline to 6 months post radiation therapy will be explored by using the 5 instruments measuring neurocognitive function. The change will be summarized graphically (using, for example, boxplots) and using mean, median or score shifting etc. This will be done for each instrument separately. Correlation coefficients will be calculated to explore potential correlation between the change in neurocognitive function from the baseline and the radiation dose to the NPC-containing region.

Spearman's rank correlation coefficient will be calculated to explore an association between the closest distance (either X-, Y-, or Z-) of the planning tumor volume to the spared NPC-containing niche and the mean, minimum, and maximum radiation dose to this region.

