TITLE: A Prospective Trial of Neural Progenitor Cell Sparing Radiation Therapy Plus Temozolomide for Newly Diagnosed Glioblastoma Multiforme

Research Site:	The Johns Hopkins University School of Medicine
Principal Investigator:	[name]., M.P.H. Department of Radiation Oncology [name] [contact] [contact] Email: [contact]
Co-Investigators:	[name]., Department of Radiation Oncology [name]., Department of Medical Oncology [name]., Department of Neuropsychology [name], N.P., Department of Oncology [name]., Department of Oncology [name]., Ph.D., Department of Oncology [name]., Department of Neurosurgery [name]., Department of Neurology [name]., Department of Psychiatry

Statistician:

[name]., M.S. [contact] Email: [contact]

Study Coordinators:

[name] [contact] [contact]

Research Nurses:

[name], R.N., B.S.N. [contact] [contact] [name] [contact] [contact]

[name], R.N.,

[contact]

[contact]

[contact] [contact]

> [name], R.N. [contact] [contact]

[name], B.S.

SCHEMA

Patient Eligibility: (See Section 3)

Newly diagnosed, histologically confirmed glioblastoma multiforme. Radiation and medical oncologist recommends adjuvant radiation plus temozolomide. Must begin therapy within 12 weeks of biopsy or surgery. No prior brain radiation. Age \geq 18 years. KPS > 60%. Signed informed consent.

Treatment Plan: (See Section 5)

Required sample size: 30 patients Anticipated accrual: 4-5 patients per month

TABLE OF CONTENTS

SC	HEM	P	age ii
ыc		•	11
1.	OBJE	CTIVES	1
	1.1	Primary Objectives	1
	1.2	Secondary Objectives	1
2.	BACH	KGROUND	1
	2.1	Study Disease and Rationale	1
	2.2	Temozolomide	3
	2.3	Correlative Studies Background	3
3.	PATI	ENT SELECTION	5
	3.1	Eligibility Criteria	5
	3.2	Exclusion Criteria	6
	3.3	Inclusion of Women and Minorities	6
4.	REGI	STRATION PROCEDURES	6
5.	TREA	ATMENT PLAN	7
	5.1	Surgery and Chemotherapy	7
	5.2	Radiation	7
	5.3	Duration of Follow Up	9
	5.4	Criteria for Removal from Study	9
6.	STUE	DY CALENDAR	10
7.	MAN	AGEMENT OF TOXICITY	11
	7.1	Acute Toxicity	11
	7.2	Late Toxicity	13
8.	STAT	ISTICAL CONSIDERATIONS	14
	8.1	Study Design/Endpoints	14
	8.2	Sample Size/Accrual Rate	15
	8.3	Stratification Factors	15
	8.4	Statistical Methods of Analysis	15
	8.5	Interim Disease Progression Monitoring	16
9.	ADVI	ERSE EVENTS AND REPORTING	17
	9.1	Definition of Adverse Event	17
	9.2	Radiation Related Adverse Event	17
	9.3	Chemotherapy Related Adverse Event	18

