5.3 Duration of Follow Up

Patients will be followed either at Johns Hopkins Hospital or an outside facility until death or the time of data analysis. It is preferred that MRIs be performed at Johns Hopkins Hospital but they may also be performed at outside facilities as necessary for insurance, scheduling, or other reasons.

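### The primary rate divides by all patients with no class for unknown or unassessable niche status, which dilutes downward a rate where low is good

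*Combined protocol and SAP*

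**What the plan says.** Section 8.4 states "All analysis will be based on the Intend-To-Treat (ITT) principle", gives the primary estimate as a binomial proportion with an exact interval ("The proportion of patients with LR in the avoidance region of the NPC will be estimated along with the exact 95% confidence interval"), and adds "All patients will count towards assessment of all objectives". The schema gives the planned size: "Required sample size: 30 patients". The 25% rate is judged by the lower limit of the exact 95% interval.

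Section 8.1.2 sets the endpoint: "Site of local recurrence at 1 year post radiation therapy will be recorded for each patient". The three classes are recurrence inside the avoidance structure, recurrence outside it, and "3) No local recurrence". No class covers patients who were not assessed or had no structure to assess.

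Four other places decide who can be assessed:
- Section 5.3: "Patients will be followed either at Johns Hopkins Hospital or an outside facility until death or the time of data analysis". No 12-month minimum is stated for the final analysis; the 6-month minimum in section 8.5 serves the interim rule only.
- Section 5.2.4: the structure to be spared is "A portion of the NPC-containing niches which is >2 cm from the PTV". Sections 3.1 and 3.2 do not require that a patient has any such tissue.
- Section 5.4: patients may withdraw at any time, and may be removed for toxicity or intercurrent illness.
- Section 6: the calendar marks brain MRI at 6 and 12 months, and footnote 7 makes it discretionary only after 12 months. The text above the table leaves follow-up MRI to the provider without that limit.

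The only sensitivity analysis named for the primary endpoint concerns the 2 patients who received mebendazole. A per-protocol analysis is allowed but not defined.

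**The concern.** A patient whose niche status at 1 year is unknown, or who has no spared niche and so cannot have the event, stays in the denominator and cannot enter the numerator. In an efficacy trial, counting unknowns as failures is conservative. Here the event is the harm, so the same all-patient convention works in favour of the technique.

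The rate matters beyond this trial. Section 2.1 makes a planned randomized trial conditional on finding that sparing does not worsen recurrence in the spared region. The same count drives the interim stopping rule in section 8.5.

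**Working it through.** **Inputs from the documents.** N = 30 (schema; section 8.5). Threshold 25% by the lower exact 95% limit (sections 8.2.1, 8.4). Median time to progression 8.5 months (section 8.5). Median survival 14.6 months and 27% alive at 2 years (section 2.1). Radiation 60 Gy in 2 Gy fractions, five per week, which is 6 weeks (section 5.2.1).

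**Assumed, because the documents give nothing.** Fraction lost by 12 months: 10-30%. Fraction unobserved and scored as non-events, u: 0-40%. Patients without a niche: 1 to 6.

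**The plan's own figures.** N = 30 cannot be recomputed, since the entropy criterion and the variation are not quantified. The one checkable figure on the same count is the 0.56 stopping probability at a true 30%. Exact enumeration of the two listed boundaries (4 of 10, 7 of 20) gives 0.485; adding a look at 10 of 30 gives 0.561. That mismatch is a separate matter.

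**1. The rule as written.** The exact lower limit is 22.7% at 12/30 and 25.5% at 13/30. The 25% rate is therefore rejected only at 13 or more of 30.

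**2. Dropout.** Take exponential progression with rate a = ln 2/8.5 = 0.0815 per month, and independent exponential dropout with rate b = -ln(1-d)/12. Niche recurrence is assumed to follow the timing of progression overall. The share of 1-year events that is seen is [a/(a+b)] × [1 - exp(-12(a+b))] / [1 - exp(-12a)].

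| d | share seen | true 30% reads | true 25% reads |
|---|---|---|---|
| 10% | 0.957 | 28.7% | 23.9% |
| 20% | 0.912 | 27.4% | 22.8% |
| 30% | 0.865 | 26.0% | 21.6% |

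**3. Effect on the decision.** If a fraction u is unobserved, has the same underlying rate p, and is scored as a non-event, the expected crude rate is p(1-u). The chance of acceptance is P(X ≤ 12), with X binomial(30, p(1-u)).

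| u | true 30%: crude rate, P(accept) | true 40%: crude rate, P(accept) |
|---|---|---|
| 0 | 30%, 0.916 | 40%, 0.578 |
| 10% | 27%, 0.961 | 36%, 0.744 |
| 20% | 24%, 0.985 | 32%, 0.871 |
| 30% | 21%, 0.995 | 28%, 0.948 |
| 40% | 18%, 0.999 | 24%, 0.985 |

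Part of the rise at 40% is only lost information. With 24 evaluable patients as the denominator (u = 20%), acceptance is 0.650. The step from 0.578 to 0.650 is smaller N; the step from 0.650 to 0.871 is dilution.

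The interim rule is diluted too. At a true 40%, the chance of stopping falls from 0.802 (u = 0) to 0.557 (u = 20%) and 0.273 (u = 40%).

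**4. Patients without a niche.** With 7 recurrences, 7/30 = 23.3%. Excluding 1, 3 or 6 patients who cannot have the event gives 7/29 = 24.1%, 7/27 = 25.9% or 7/24 = 29.2%. The point estimate can cross 25%, but the stated decision need not change: the lower limit is 9.9% for 7/30 and 11.1% for 7/27.

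**5. Deaths.** One year after radiation is about 13.5 months from its start. Taking the survival clock from the start of radiation (an assumption), an exponential with median 14.6 months gives 1 - 0.5^(13.5/14.6) = 47% dead. A Weibull through 50% at 14.6 and 27% at 24 months also gives 47%. That is about 14 of 30.

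**6. Recurrence never imaged before death.** If an assumed 20% of niche recurrences are never imaged, a true 30% reads 0.30 × 0.80 = 24%. A cumulative incidence that counts every death without a recorded niche recurrence as competing also gives 24%, because those deaths remain non-events.

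**The case against.** The strongest reply is that the plan nowhere says that unknown outcomes count as non-recurrence. The all-patients sentence opens the paragraph on mebendazole and is not a missing-data rule. Section 8.1.2 intends a 1-year site for every patient, section 5.2.7 has all treated patients followed per the calendar, and section 8.1.3.2 expects a spared-region volume and dose for each patient. This stands in part: the scoring is inferred. If another handling was intended, however, it is unwritten and could be chosen after the data are seen.

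A reader might infer that the 14 or so expected deaths are 14 misclassified outcomes. The documents do not support that. Median progression (8.5 months) comes well before median survival (14.6 months), so many who die will already have a recorded site. A patient adequately imaged before death without niche recurrence is a true non-event, and dropping all deaths would overcorrect.

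A reader might also infer that the bias is shown to carry the result across 25%. It is not. None of the dropout scenarios takes a true 30% below 25%, the missing-niche example leaves the stated decision unchanged, and at a true 30% acceptance is already 0.916 with no dilution.

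It is also fair to say that cumulative incidence alone does not recover recurrences never imaged before death, which is why the fix needs bounds as well. The objection that competing-risk methods are excessive for a 30-patient pilot carries less weight: with complete follow-up and a scan before every death, the estimate equals the planned proportion.

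**Conclusion.** The concern holds as a gap with a known direction and an unknown size. The all-patient denominator and the three-class endpoint leave patients with unknown or impossible niche recurrence nowhere to go except the non-event side, and that favours the technique. This rests on inferring the scoring from sections 8.1.2 and 8.4.

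Every figure for the size rests on an assumed unobserved fraction, on independent dropout, and on the unobserved having the same underlying rate. On those terms the shift is modest for dropout alone (1 to 4 percentage points). It is larger if a fifth of patients are unobserved, and the effect on the decision is greatest at true rates near 40%, where acceptance goes from 0.58 to 0.87. The documents do not support a stated amount of bias, nor a claim that the conclusion would reverse. The plan should be changed before analysis, but this does not invalidate the trial.

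**What to change.** 1. **At-risk set.** Base the primary estimate on patients whose recorded NPC_for_sparing volume is above zero, and report how many are excluded. The volume is already collected.
2. **Estimator.** Report the 1-year cumulative incidence of spared-region recurrence (Aalen-Johansen). Censor loss and short follow-up at the last MRI. Count a death as competing only if an MRI within a prespecified window before it shows no niche recurrence. Other deaths have unknown status and are censored at the last MRI; since that censoring may be informative, item 3 is needed.
3. **Bounds.** Keep the exact binomial, once with all unknown-status patients (including deaths without a recent scan) as non-events and once as events. For example, with 5 recurrences and 6 unknowns: 5/30 = 16.7% (5.6-34.7%) and 11/30 = 36.7% (19.9-56.1%).
4. **Data cutoff.** Run the primary analysis only when every patient has died, been lost, or reached 12 months after radiation.

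The text and calendar on follow-up MRI in section 6 should also be reconciled, because they decide how many outcomes are unknown.

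The cost is SAP wording and one standard analysis on data already planned, a slightly wider interval, and possibly a less favourable rate.
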